Title:

Effect of Pomegranate Seed Powder on
markers of Metabolic Syndrome

NCT:

Not Assigned yet

Submission Date:

Uploaded here on 21st June, 2023

STATEMENT OF PROBLEM

A number of chronic disorders can lead to metabolic syndrome, which has been identified as one of the key risk factors for the epidemic of type 2 diabetes and cardiovascular diseases in the twenty-first century. Thus, it's a high time to mitigate the prevalence of these risk factors to overcome metabolic syndrome.

Objective:

To evaluate the effectiveness of pomegranate seed powder supplementation in preventing metabolic dysfunction and its main risk factors, such as hypertension and cardiovascular illnesses.

Study Protocol

Type of Study

This trial is prospective clinical type.

Supplement preparation

Pomegranate seeds and arils will be separated, and then the seeds will be dried for 15 days in a lab environment. Later, a mechanical grinder will be used to powder the dried seeds. PS powder (PSP) will be packed in a capsule form, 5 g in each.

Participants

The population under study will be consisted of people suffering with any of the three metabolic impairments; Insulin resistance, obesity, disturbed glucose level, hyper-cholesterol, hypertension and higher blood pressure. Exclusion criteria will be critically ill or hospitalized patients and individuals with digestion and absorption issues.

Span of study

The clinical trial on the 50 patients of metabolic syndrome will be conducted for the duration of 8 weeks with the supplementation of PSP capsule, twice a day.

Outcome Evaluation

Blood pressure, total cholesterol, and triglycerides (TG) will be measured at the enrollment point (i.e., baseline) and at the end of the 8-week intervention period. Fasting blood glucose (FBG), glycated haemoglobin (HbA1c), and triglycerides (TG) will be measured at the enrollment point (i.e., baseline). A fresh blood sample from a vein will then be taken and examined. A calibrated digital weight scale will also be used to check the patient's weight. Detail of all data collected is as follows:

Anthropometric Measurements:

- Weight
- Height
- Skin fold Thickness

Biochemical Evaluation:

- Blood Pressure
- Fasting Blood Glucose
- Total Cholesterol
- Triglycerides

Clinical Evaluation:

- Obesity

Statistical Analysis Plan

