Using one-way ANOVA, the statistical significance of the host parameter data will be determined (SPSS Inc., Chicago, IL, USA). When the p-values are less than 0.05, differences are considered significant. Statistical analyses will be carried out in the R programming environment for data sequencing. For both quantitative and qualitative variables, data will be displayed as means \pm SD or frequency (percent), respectively.

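### Nothing secures a week-8 value from patients who stop the capsules or ties both means to the same people, so selective dropout shifts the before-after difference, though seldom to significance

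*Combined protocol and SAP*

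**What the plan says.** The Span of study section describes a single set of patients: "The clinical trial on the 50 patients of metabolic syndrome will be conducted for the duration of 8 weeks". It mentions no comparator and does not state the number of arms.

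Outcome Evaluation says that blood pressure, total cholesterol and triglycerides "will be measured at the enrollment point (i.e., baseline) and at the end of the 8-week intervention period". For fasting glucose and HbA1c the only stated time is enrolment.

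The Statistical Analysis Plan is one short paragraph. The test is given as "Using one-way ANOVA, the statistical significance of the host parameter data will be determined", the threshold as "When the p-values are less than 0.05, differences are considered significant", and the presentation as "data will be displayed as means \pm SD or frequency (percent), respectively". It contains no pairing, change score or subject term. The document has no definition of the analysis population, no rule for missing values and no statement on patients who stop the capsules.

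**The concern.** A one-way ANOVA of baseline against week 8 treats the two visits as two independent samples and uses every value present in each. If 50 patients are measured at enrolment and fewer at week 8, the two means describe different people. When the missing patients had worse values, the week-8 mean falls even if no patient changed.

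This is a bias from who remains. It is separate from the precision lost by ignoring pairing. No comparator is described, so there is no second arm in which similar dropout could offset it. Week-8 values that are not collected cannot be recovered later.

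**Working it through.** The plan gives no power, effect size, SD or dropout rate, so it has no derived figure to reproduce. The check is of the mechanism and its size.

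**Inputs from the document:** n = 50 (Span of study); measurement at baseline and week 8 (Outcome Evaluation); threshold 0.05 (Statistical Analysis Plan), so 2.5% nominal in the direction of improvement.

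**Assumed, because the document is silent:** dropout share d = 10%, 20%, 30%; gap k = 0.5 to 1 SD between leavers and stayers, leavers worse and the gap lasting; within-person correlation ρ = 0.6 to 0.8; true change zero for everyone. One SD is the spread within leavers or within stayers.

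**Step 1: shift in the displayed difference.** Let S and L be the baseline means of stayers and leavers. The baseline mean of all patients is (1 − d)S + dL. With no change, the week-8 mean is S. The expected difference is S − [(1 − d)S + dL] = −d(L − S) = −dk.

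| Dropout | k = 0.5 SD | k = 1 SD |
|---|---|---|
| 10% | −0.05 | −0.10 |
| 20% | −0.10 | −0.20 |
| 30% | −0.15 | −0.30 |

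For scale only: with an assumed SD of 15 mmHg, 0.05 to 0.30 SD is 0.75 to 4.5 mmHg. With an assumed triglyceride SD of 80 mg/dL it is 4 to 24 mg/dL.

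**Step 2: does the unpaired ANOVA call it significant?** Take d = 20%, k = 1, so 50 values against 40.

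- Baseline variance: 1 + k²d(1 − d) = 1 + 0.16 = 1.16. Pooled variance: (49 × 1.16 + 39 × 1)/88 = 1.089.
- The ANOVA's standard error: √[1.089 × (1/50 + 1/40)] = 0.221. Difference needed: 1.987 × 0.221 = 0.440 SD.
- Actual SD of the difference: √(1/50 + 1/40 − 2ρ/50) = 0.145 at ρ = 0.6 and 0.114 at ρ = 0.8.
- Chance of a false significant improvement: (0.440 − 0.200)/0.145 = 1.66, upper tail 4.9%; 0.240/0.114 = 2.10, upper tail 1.8%.

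Simulation agrees (ρ = 0.8 to 0.6; repeat runs differ by a few tenths of a percentage point):

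| Dropout | k = 0.5 SD | k = 1 SD |
|---|---|---|
| 20% | 0.3% to 1.4% | 1.8% to 4.9% |
| 30% | 1.0% to 3.0% | 9.5% to 15% |

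With no dropout the rate is about 0.1% or less. The test is conservative because its standard error (0.221) ignores the positive correlation that makes the true spread 0.114 to 0.145. A gap of 1.5 SD, outside the main range, gives 8% to 12% at 20% dropout and 36% to 38% at 30%.

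**Step 3: a paired test on completers.** With both means from the same patients, the composition shift is 0.00 SD in every simulated setting, and false improvement is 2.1% to 2.9%. Dropout may instead depend on the patient's own response. Let leaving correlate r with a worse change, and let the 20% with the highest tendency to leave go. Completers' mean change moves by r × 0.35 SD of change, with 40 completers.

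- r = 0.3: 0.105 × √40 = 0.66; 1.96 − 0.66 = 1.30; upper tail about 9.7%.
- r = 0.5: 0.175 × √40 = 1.11; 1.96 − 1.11 = 0.85; upper tail about 20%.

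Simulation gives about 10% to 21% at 20% dropout, and 14% to 33% at 30%. When all 50 patients are measured at week 8, the rate returns to about 2.5%.

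**Step 4: the same response-related dropout under the unpaired ANOVA.** False improvement is 0.1% to about 1.2% at 20% dropout and 0.2% to about 2.4% at 30%, below nominal throughout.

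**The case against.** **The week-8 sentence already covers everyone.** It makes no exemption for patients who stop, so the requested visit clarifies the schedule and adds no new one. That stands. But the sentence sets a time; it does not say that stoppers are recalled or analysed.

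**Every driver of the bias is assumed.** This stands. The document gives no dropout rate, gap, SD or correlation. Random dropout causes no mean shift, and loss of healthier patients would hide benefit.

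**The comparison is inferred.** This also stands. The plan names no groups for the ANOVA, and the undefined comparison is a prior defect.

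**The planned test protects against false significance.** Largely true. A reader might infer that dropout alone gives the named ANOVA a 10% to 20% false-improvement rate. The document does not support that: those rates belong to a paired completer test, which the plan does not name. Under the unpaired ANOVA, rates within the assumed range are mostly below 2.5%. They reach about 5% at 20% dropout with a 1 SD gap, and are clearly above nominal only near 30% dropout with a gap of that size. The conservatism does not correct the displayed means, which shift whatever the p-value.

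**Pairing alone would do.** It would not. It removes the composition shift but leaves dropout related to response.

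**Conclusion.** The point holds as a bias in the displayed before-after difference: 0.05 to 0.30 SD for 10% to 30% dropout and a 0.5 to 1 SD gap, with its direction set by whether leavers are worse or better than stayers. It rests on reading the ANOVA as baseline against week 8 and on the assumed ranges above.

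Two stronger conclusions are not supported. One is that the planned test will often declare a false improvement; for most of the assumed range it will not. The other is that the bias must favour the supplement; the document says nothing about who would leave.

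The risk of false significance grows if the analysis is changed to a paired test while stoppers remain unmeasured: about 10% to 21% at 20% dropout if leaving correlates 0.3 to 0.5 with a worse change. Better analysis and complete follow-up therefore have to be adopted together. This should be settled before enrolment.

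**What to change.** 1. State that every enrolled patient is measured at the scheduled week-8 visit whether or not capsules were continued, and is included in the analysis.
2. Replace the one-way ANOVA with a paired analysis of within-patient change, and report the baseline mean, week-8 mean and change from the same patients. Adopt this only together with item 1.
3. If any week-8 values are missing, report how many, and give a tipping-point analysis: how much worse the unmeasured patients' changes would have to be for the result to lose significance. Assigning them zero change is not a substitute. In simulation it left false improvement at about 10% to 20% at 20% dropout, because the mean and its standard error shrink together.

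These apply to outcomes with a week-8 measurement. The text schedules one for blood pressure, total cholesterol and triglycerides; none is stated for fasting glucose or HbA1c, so the plan should say whether those are repeated.

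The cost is a few sentences, some reminder calls, and possibly a smaller estimated effect because patients who stopped are counted.

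### One-way ANOVA with every p<0.05 called significant, no defined comparison and no primary outcome: depending on how it is run, the plan either ignores the pairing and loses power or leaves several unranked chances of a positive claim

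*Combined protocol and SAP*

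**What the plan says.** The inferential plan is two sentences in the Statistical Analysis Plan section. The method: "Using one-way ANOVA, the statistical significance of the host parameter data will be determined". The decision rule: "When the p-values are less than 0.05, differences are considered significant". The host parameters are not listed or defined, and the groups or time points that the ANOVA compares are not given.

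The protocol sections supply the rest:

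- **Objective:** "To evaluate the effectiveness of pomegranate seed powder supplementation in preventing metabolic dysfunction and its main risk factors". This covers several risk factors and singles out no marker.
- **Span of study:** "The clinical trial on the 50 patients of metabolic syndrome will be conducted for the duration of 8 weeks", with all described as receiving the capsule. No second group, placebo or allocation is mentioned.
- **Outcome Evaluation:** two visits are stated for three markers: "Blood pressure, total cholesterol, and triglycerides (TG) will be measured at the enrollment point (i.e., baseline) and at the end", meaning week 8. Fasting glucose and HbA1c are stated at baseline only. The list introduced by "Detail of all data collected is as follows" adds weight, height, skinfold thickness and obesity, without visit times.

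The document contains no primary outcome, order of testing, multiplicity adjustment or definition of trial success.

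**The concern.** Two gaps interact. The first is the test. With one set of 50 patients measured twice, the natural comparison is within patient. One-way ANOVA of baseline against week 8 treats the two sets of values as if they came from different people, so its error rate is not the nominal 5% and real changes are more easily missed.

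The second is the decision rule. With a valid test for each marker, one broad objective has at least three unranked chances of a result called significant. Nothing stops the marker to be emphasised from being chosen after the data are seen, and one p<0.05 among several is weaker evidence than its nominal level suggests.

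The gaps pull in opposite directions: the unpaired test hides the multiplicity, and correcting the test exposes it. They therefore need one joint correction.

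**Working it through.** The plan states no overall error rate, power or sample-size calculation, so there is no figure of its own to reproduce.

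**Inputs from the document:** threshold 0.05 (Statistical Analysis Plan); 50 patients (Span of study); three markers with both visits stated, namely blood pressure, total cholesterol and triglycerides (Outcome Evaluation). Sidedness is not stated. The F test is non-directional, so for two time points 0.05 means 0.025 in each direction.

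**Assumptions:** 50 patients with both values; normal data with equal variance at the two visits; pre-post correlation r of 0.3, 0.5 or 0.7; between-marker correlation of 0, 0.3 or 0.5.

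**Step 1. ANOVA run as baseline versus week 8, unpaired.** The test takes the variance of the mean difference to be 2σ²/50. The true variance is 2σ²(1−r)/50. With no change, the test therefore rejects roughly when |Z| > 1.96/√(1−r). At r = 0.3 that cut-off is 1.96/0.837 = 2.34, which gives about 1.9%. Simulation at n = 50 gives:

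| r | per-test error p | three independent markers, 1−(1−p)³ |
|---|---|---|
| 0.3 | 2.0% | 5.8% |
| 0.5 | 0.6% | 1.9% |
| 0.7 | 0.05% | 0.2% |

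**Step 2. Power on the same reading.** A paired t-test with n = 50 at two-sided 0.05 has 80% power for a mean change of 0.404 SD of the change. At that change the unpaired ANOVA has power 69% / 52% / 24% for r = 0.3 / 0.5 / 0.7.

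**Step 3. Each marker validly tested, for example paired.** For three independent markers with no true change:

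- any direction: 1−(1−0.05)³ = 1−0.8574 = 14.3%;
- direction of benefit: 1−(1−0.025)³ = 1−0.9269 = 7.3%, against 2.5% for one test.

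With equally correlated normal statistics:

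| between-marker correlation | any direction | benefit only |
|---|---|---|
| 0 | 14.3% | 7.3% |
| 0.3 | 13.6% | 6.8% |
| 0.5 | 12.5% | 6.3% |

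Positive correlation lowers both columns. Negative correlation can raise the benefit-only figure slightly, to no more than 3 × 2.5% = 7.5%.

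**Step 4. Sensitivity to the count.** If systolic and diastolic pressure were tested separately (four tests, an assumption), the any-direction range is 15.6% to 18.5% and the benefit-only range 7.8% to 9.6%, for correlation 0.5 to 0.

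**Step 5. Check of the remedy.** With no true change in any marker, a primary at 0.05 followed by Holm on the rest only if the primary is significant gives 5.0% overall, for three or four markers at each correlation above. Holm at a further 0.05 without that condition gives 8.5% to 9.7%.

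**The case against.** The strongest reply is that the 14.3% does not describe this plan. The only named test is one-way ANOVA, and with one described set of patients its unpaired reading keeps the overall rate at 5.8% or less for r of 0.3 or more. A reader might infer that the plan as written runs a false-positive risk of about 14%. The document does not support that, because the comparison is undefined and the figure needs a valid test that the plan does not specify. This part of the objection stands.

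It also stands that no any-marker success rule is stated. A reader might infer that one significant marker would count as success, but the text says only when a difference is called significant. Reporting marker by marker is equally open.

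The number of tests is uncertain too. Triglycerides appear in two adjacent sentences with different timing, and the timing of several listed measures is not given. Three is the number that the stated visits support. Larger counts need assumptions.

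Finally, the missing comparator is the larger limit. Patients enrolled for impairments such as high cholesterol or hypertension may show lower values on re-measurement without any supplement effect, and naming a primary outcome does not remove that.

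None of this rescues the rule as written. On the unpaired reading it wastes information, and on a valid reading it leaves unranked tests. The document does not call the trial exploratory: the aim is to evaluate effectiveness and differences are to be called significant.

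**Conclusion.** The concern holds in a conditional form. If the ANOVA compares the two visits as independent groups, the fault is a mismatched test: per-test error of about 2% / 0.6% / 0.05% and power of about 69% / 52% / 24% in place of 80%, at assumed pre-post correlation 0.3 / 0.5 / 0.7. Multiplicity inflation is then not the issue. If each marker is validly tested, the chance of at least one false positive among three is about 12.5% to 14.3%, or 6.3% to 7.3% in the direction of benefit, for between-marker correlation 0.5 to 0. Those percentages illustrate scale and are not the trial's error rate, which cannot be derived until the comparison and the list of tests are fixed.

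The plan should be changed on either reading. Confidence is medium, because the size depends on assumed correlations and on a comparison that the document leaves open.

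**What to change.** Before analysis:

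1. State the comparison. If the trial is single-arm, replace one-way ANOVA with the within-patient change from baseline to week 8 (paired t-test with 95% CI). If there is a second group, describe it and specify the between-group comparison.
2. Name one primary outcome measured at both visits and test it at two-sided 0.05. The choice is the sponsor's; if it is blood pressure, say systolic or diastolic.
3. Report the remaining markers as exploratory, with 95% CIs and no significance claim. Holm on them, only if the primary is significant, is an acceptable alternative.
4. List which markers are analysed and at which visits.
5. Say in the conclusion that, without a comparator, a significant before-after change cannot be attributed to the supplement.

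The cost is plan wording and, if single-arm, a change of test. No new data are needed for the three markers with both visits stated, but each patient's two values must be linked. Some secondary markers with p<0.05 could no longer be called significant; under the Holm alternative none could be if the primary fails. The 50 patients have no stated power basis: with 50 completers, the paired analysis has 80% power for a mean change of about 0.40 SD of the change.

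### The plan names no mean within-patient change with a confidence interval, so the precision of the 8-week change cannot be read from the planned display and one-way ANOVA

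*Combined protocol and SAP*

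**What the plan says.** The Statistical Analysis Plan is one short paragraph. It gives a test, "Using one-way ANOVA, the statistical significance of the host parameter data will be determined", a decision rule, "When the p-values are less than 0.05, differences are considered significant", and a display rule, "For both quantitative and qualitative variables, data will be displayed as means" with SD for quantitative variables, or frequency and percent for qualitative ones. It does not name a change from baseline, an SD of change, a standard error or a confidence interval.

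The Span of study section sets the size and duration: "The clinical trial on the 50 patients of metabolic syndrome will be conducted for the duration of 8 weeks". All of these patients appear to take the supplement. No control group, target difference, power or SD is given.

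Under Outcome Evaluation, blood pressure, total cholesterol and triglycerides "will be measured at the enrollment point (i.e., baseline) and at the end of the 8-week intervention period". Fasting glucose and HbA1c are given a baseline measurement only. Triglycerides also appear in that baseline-only sentence. No week-8 time is stated for weight or skinfold thickness.

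**The concern.** The objective is to judge how effective the supplement is, so a reader needs both the size of the change and how well it is known. As described, all patients take the supplement and the main markers are measured twice in the same people, so the natural contrast is change within patients. An SD at each visit describes how patients differ from one another. It does not describe the uncertainty of the mean change, because that depends on how strongly each patient's two values are related.

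With no target difference or power stated, the reader has nothing else to lean on when p exceeds 0.05. The result could mean little or no change, or a change measured too imprecisely to tell. The display and test, followed as written, do not separate these.

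**Working it through.** The documents give no precision or power figure to reproduce, so this is an illustration under stated assumptions.

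**Inputs**
- From the documents: n = 50 and a 0.05 threshold. Sidedness is not stated; two-sided is assumed.
- Assumed: complete pairs, the same SD (s) at both visits, and a baseline to week-8 correlation r that is varied because no value is given.
- Also assumed: the ANOVA compares the two visits as independent groups. The plan does not say what the groups are.

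**Formulas**
- Mean change = week-8 mean − baseline mean (complete pairs).
- SD of change = s·√(2(1−r)).
- 95% half-width = t(0.975, 49) × SD of change / √50, with t(0.975, 49) = 2.0096. Since 2.0096/√50 = 0.284, the half-width is 0.284 × SD of change.

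**Range of precision behind one display** (assumed s = 15 mmHg)

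| r | SD of change | 95% half-width |
|---|---|---|
| 0.3 | 15 × √1.4 = 17.7 | 5.04 |
| 0.5 | 15 × √1.0 = 15.0 | 4.26 |
| 0.7 | 15 × √0.6 = 11.6 | 3.30 |
| 0.9 | 15 × √0.2 = 6.7 | 1.91 |

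The widest is 5.04/1.91 = 2.6 times the narrowest, yet the printed mean ± 15 is the same in every row.

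**Does the planned p-value fill the gap?** Take s = 10 at both visits and a difference in means of −2.5.

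| r | 95% interval for change | Paired p |
|---|---|---|
| 0 | −6.52 to 1.52 | 0.22 |
| 0.5 | −5.34 to 0.34 | 0.083 |
| 0.8 | −4.30 to −0.70 | 0.007 |
| 0.9 | −3.77 to −1.23 | 0.0002 |

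A one-way ANOVA on two independent groups of 50 uses a standard error of 10 × √(2/50) = 2.0, so t = 2.5/2.0 = 1.25 and p = 0.21 in all four rows. That p-value is fixed by the means and SDs already displayed and adds nothing about r. In the last two rows it is non-significant although the paired interval excludes zero.

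**What a non-significant result could hide.** For a paired analysis of 50 complete pairs, the difference detectable with 80% power (noncentral t) is 0.57 s at r = 0, 0.40 s at r = 0.5, 0.26 s at r = 0.8 and 0.18 s at r = 0.9. If only 40 patients had both values (an assumption; no dropout is stated), the half-width would run from 0.45 s (r = 0) to 0.14 s (r = 0.9), against 0.40 s to 0.13 s with 50.

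**The case against.** The strongest reply is that this is a gap in a display rule, not a barrier to inference. Much of it stands.

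- A reader might infer that the size of the change is lost as well. It is not: with complete pairs the mean change is the difference of the visit means. It fails only if the two means rest on different patients. The spread of individual changes is lost either way.
- A reader might infer that precision is lost whatever test is used. That is not so. An exact paired p-value would return the interval: in the example at r = 0.5, p = 0.083 gives t of about 1.77, a standard error of 2.5/1.77 = 1.41 and the interval −5.34 to 0.34. But the plan names one-way ANOVA and no paired test.
- A reader might infer that the plan forbids anything beyond means and SDs. It does not; it simply plans no interval. Nor does it say whether the means are per visit or of the changes. If they were of the changes, the SD of change would be shown and an interval could be computed from it and the number of pairs.
- The patient-level data would allow an interval at any time, so a non-significant result is uninformative as reported, not beyond interpretation.
- The SD of 15 and every r are assumptions.

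None of this supplies an interval under the plan as written. Changing to a paired test alone would still leave none planned.

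**Conclusion.** The point holds in a limited form. Followed as written, with means and SDs shown per visit and an ANOVA that treats visits as independent groups, the plan leaves the precision of the within-patient change unreadable. At n = 50 and an assumed SD of 15 mmHg, the 95% half-width could be anywhere from 5.0 mmHg (r = 0.3) to 1.9 mmHg (r = 0.9). A non-significant result would be uninformative as reported.

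This rests on a single-group, two-visit reading that the documents imply but do not spell out, and on equal SDs and complete pairs. It applies to blood pressure, total cholesterol and triglycerides, the markers with a stated week-8 measurement. Because an interval from paired changes can lead to a different conclusion from the planned ANOVA, the change should be made and is more than a matter of presentation.

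**What to change.** For each quantitative outcome measured at both visits (as written: blood pressure, total cholesterol and triglycerides), replace the display rule with: number of complete pairs; baseline mean (SD); week-8 mean (SD); mean within-patient change; SD of change; 95% confidence interval for the mean change. State that the conclusion about before-after change is drawn from that interval. Keep mean ± SD, and frequency with percent, for describing patients at baseline.

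The cost is about one sentence in the Statistical Analysis Plan, with no new data for those three markers. Fasting glucose, HbA1c, weight and skinfold thickness could be reported this way only if a week-8 measurement is taken, which the text does not state. The report should also say that the interval describes before-after change and, with no control group described, does not by itself measure the effect of the supplement.

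### Triglycerides: the SAP plans ANOVA and mean ± SD with no pairing or transformation; a paired log-scale analysis would usually gain power, mainly from the pairing (minor)

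*Combined protocol and SAP*

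**What the plan says.** The Statistical Analysis Plan is one short paragraph. On testing: "Using one-way ANOVA, the statistical significance of the host parameter data will be determined". On significance: "When the p-values are less than 0.05, differences are considered significant". On presentation: "data will be displayed as means" with SD for quantitative variables. It does not name the groups that the ANOVA compares, and it mentions no paired analysis, transformation, distribution check, rank test, median or geometric mean.

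Under Span of study: "The clinical trial on the 50 patients of metabolic syndrome will be conducted for the duration of 8 weeks". One supplemented group is described and no control arm. Type of Study adds only "This trial is prospective clinical type".

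Outcome Evaluation gives two statements on timing. The first is "triglycerides (TG) will be measured at the enrollment point (i.e., baseline) and at the end of the 8-week intervention" period. The next is "Fasting blood glucose (FBG), glycated haemoglobin (HbA1c), and triglycerides (TG) will be measured at the enrollment point (i.e., baseline"), with no week-8 measurement named.

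**The concern.** A triglyceride concentration cannot fall below zero and has no upper limit in the plan, so a long right tail is plausible. If there is one, a few high values can dominate both the mean ± SD and a raw-scale test. Fifty patients largely protect the type I error of that test, but they do not restore the efficiency lost to the tail.

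There is a second and larger issue. Baseline and week-8 values come from the same people. A one-way ANOVA of 50 baseline against 50 week-8 values treats them as independent and discards the within-person correlation.

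At stake is the chance of detecting a real fall in one of the few markers with a stated week-8 value, in a trial whose sample size has no stated power basis.

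**Working it through.** **Inputs from the documents.** 50 patients (Span of study); triglycerides at baseline and week 8 (first timing statement, Outcome Evaluation); one-way ANOVA, 0.05 threshold, mean ± SD (Statistical Analysis Plan). No power, effect size, SD or correlation is given, so there is no planned figure to reproduce.

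**Assumptions.** The ANOVA compares baseline with week 8 (the documents do not say). Triglycerides are log-normal with log-SD s = 0.4 to 0.6. CV = √(exp(s²) − 1), which is 42%, 53% and 66% at s = 0.4, 0.5 and 0.6. Log-scale correlation r is 0.5 to 0.8, the proportional fall is 15% or 20%, and there is no dropout. A two-group ANOVA is the same as a two-sided two-sample t-test.

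**Hand check of one case (s = 0.5, r = 0.7, 15% fall, log scale).**
- Effect: |ln 0.85| = 0.1625.
- Paired: SD of the difference = 0.5 × √(2 × 0.3) = 0.387. Noncentrality = 0.1625 / 0.387 × √50 = 2.97, so power is about 83%.
- Unpaired ANOVA: it uses SE = 0.5 × √(2/50) = 0.100, while the true SE is 0.387/√50 = 0.055. The statistic centres on 1.625 with SD 0.548, against a critical value of 1.984. Power ≈ P(Z > (1.984 − 1.625)/0.548) = P(Z > 0.66), about 26%. With no effect, simulation gives a rejection rate of about 0.1% instead of 5%.

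**Simulation (20,000 trials per row, power in %).**

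| log-SD | r | Fall | ANOVA raw → log | Paired raw → log |
|---|---|---|---|---|
| 0.4 | 0.5 | 15% | 48.6 → 52.7 (+4.1) | 75.3 → 80.2 (+4.9) |
| 0.5 | 0.7 | 15% | 23.7 → 26.8 (+3.1) | 74.6 → 82.4 (+7.8) |
| 0.6 | 0.7 | 15% | 11.9 → 14.0 (+2.1) | 56.4 → 67.6 (+11.2) |
| 0.6 | 0.5 | 20% | 36.4 → 43.4 (+7.0) | 62.6 → 72.7 (+10.1) |

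Repeat runs agreed to within about 1 point per cell, so the paired gain is put at about 5 to 12 points. Over all combinations of s = 0.4 to 0.6, r = 0.5 to 0.8 and the two falls, the ANOVA gain runs from about 2 to 9 points. The paired gain runs from 0, where both are near 100%, to about 12.

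**Separating the two sources.** In the second row, changing only the scale moves power from about 24% to 27%. Changing only the pairing moves it from about 24% to 75%. Doing both gives about 82 to 83%.

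**Where the log scale does worse.**
- Normal data, CV 30%, constant downward shift, paired test: 63 → 58% (r = 0.5, 10% fall) and 85 → 79% (r = 0.7, 10% fall). Across runs this is about 5 to 7 points, and less where power exceeds 90% (93 → 90% at r = 0.5, 15% fall).
- Effect only in high values (excess over the median cut by 45%, s = 0.5, r = 0.7), paired test: 51.2 → 29.6%, a loss of about 22 points.

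**Descriptive summary.** At CV 66%, mean − 2 SD = mean × (1 − 1.32) = −0.32 × mean. That is impossible for a concentration, so mean ± SD would describe such data poorly whichever test is used.

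**The case against.** The strongest objection is that nothing in the documents shows skewness. The SAP paragraph does not name triglycerides or a scale; raw-scale testing is inferred from its silence, and the statement on means concerns display only. A reader might take the mix of entry routes in Participants as evidence of a skewed sample. It is not: the only lipid entry item is high cholesterol, triglycerides are not an entry criterion, and mixed routes do not establish a right tail. This stands, and skewness is used here only as an assumption.

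A reader might also infer that moving to the log scale recovers the power lost under the planned ANOVA. It does not. Under that test it returns only a few points, and the paired gains belong to a test that the SAP does not contain.

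Nor does right skew alone favour the log scale. The gain also depends on the form of the effect, and the loss when only high values respond exceeds the largest gain found. If values are not skewed, the log scale carries a cost rather than being neutral.

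Finally, no primary outcome is named, and with the ANOVA groups undefined this is fine-tuning of one marker. That argues for a low rating, which is given. It does not remove the point: the plan ignores the repeated measurement, and the choice between a ratio and an absolute change should be fixed before data are seen.

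**Conclusion.** The point holds in a conditional form and is minor. As written, the SAP provides neither pairing nor a transformation for a marker measured twice in the same 50 patients. Given right-skewed values and a roughly proportional effect, the log scale is worth about 2 to 7 points of power in an unpaired ANOVA and about 5 to 12 in a paired test in the four main scenarios. Pairing is worth about 51 points (75 − 24) in the reference case.

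Every size rests on an assumed distribution, correlation and effect, and on reading the ANOVA as baseline against week 8. The documents do not support saying that triglycerides are skewed in this population, or that a log analysis is better under every form of effect. All of it also presupposes that a week-8 value exists. If the second timing statement governed, there would be no change to test.

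**What to change.** Add to the SAP, before any data are seen: *Triglycerides will be compared within person between baseline and week 8 on the log scale, by a paired analysis. The result will be the week-8/baseline geometric mean ratio with 95% CI. Geometric means or medians with interquartile ranges will be shown at each time. Raw means ± SD and the raw paired difference will be given as a supporting analysis.*

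Reconcile the two triglyceride timing statements in Outcome Evaluation, and state which groups the ANOVA is meant to compare.

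The cost is a few SAP sentences and no new measurements, provided that the week-8 sample is already intended. This changes the test as well as the scale, and the SAP should say so. The effect becomes a ratio rather than a difference in mg/dL, and power falls somewhat if triglycerides are not skewed, or more if only high values respond. The supporting raw analysis keeps the absolute change visible in those cases.
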